Programming Notes: The “Analysis Population” column will be replaced by a column titled “Unblinding/Crossover Remdesivir Treatment”. The first set of summaries will be for the “Unblinding” sensitivity analyses, and the second set will be for the “Crossover Remdesivir Treatment” sensitivity analyses.

Table 61: Time to Death through Day 15 and 29 by Treatment Group

Analysis Population	Study Day	Treatment Group	Median Time			HR		P-value
			n	Estimate	95% CI	Estimate	95% CI	
ITT Population	Day 15	Remdesivir (N=X)	x	x.x	x.x, x.x	x.x	x.x, x.x	x.xxx
		Placebo (N=X)	x	x.x	x.x, x.x			
	Day 29	Remdesivir (N=X)	x	x.x	x.x, x.x	x.x	x.x, x.x	x.xxx
		Placebo (N=X)	x	x.x	x.x, x.x			
Treated Population	Day 15	Remdesivir (N=X)	x	x.x	x.x, x.x	x.x	x.x, x.x	x.xxx
		Placebo (N=X)	x	x.x	x.x, x.x			
	Day 29	Remdesivir (N=X)	x	x.x	x.x, x.x	x.x	x.x, x.x	x.xxx
		Placebo (N=X)	x	x.x	x.x, x.x			

N= Number of subjects in the specified treatment group and analysis population.
n = Number of subjects who died by the specified study day.
HR is the hazard ratio from the Cox Model
P-value calculated using the Log-rank test

Table with similar format:

Table 62: Time to Death through Day 15 and 29 by Treatment Group – Unblinding and Crossover Treatment Sensitivity Analysis

Programming Notes: The “Analysis Population” column will be replaced by a column titled “Unblinding/Crossover Remdesivir Treatment”. The first set of summaries will be for the “Unblinding” sensitivity analyses, and the second set will be for the “Crossover Remdesivir Treatment” sensitivity analyses.

Table 63: Subjects Experiencing Grade 3 or 4 AEs and SAEs through Day 29 by Treatment Group– Treated Population

Safety Event Outcome	Remdesivir (N=X)			Placebo (N=X)			P-value
	n	%	95% CI	n	%	95% CI	
Grade 3 or 4 AE	x	x	x.x, x.x	x	x	x.x, x.x	0.xxx
SAE	x	x	x.x, x.x	x	x	x.x, x.x	0.xxx

N = Number of Subject in the Treated Population.
n = Number of subjects in a given treatment group who experienced the specified safety event outcome.
95% CI calculated using C-P/Blaker method
P-value calculated using Barnard's Exact Test

Table 64: Analysis of Time to Death, SAEs, or Grade 3 or 4 AEs by Treatment Group – Treated Population

Treatment Group	n	Median Time		HR		P-value
		Estimate	95% CI	Estimate	95% CI	
Remdesivir (N=X)	x	x.x	x.x, x.x	x.x	x.x, x.x	x.xxx
Placebo (N=X)	x	x.x	x.x, x.x			

N= Number of subjects in the Treated Population.

n = Number of subjects who died or experienced SAEs, Grade 3 or 4 AEs, or Discontinuation of Study Infusions.

HR is the hazard ratio from the Cox Model

P-value calculated using the Log-rank test

Table 65: Abnormal Laboratory Results of Grade 3 or 4 by Parameter, Maximum Severity, Time Point, and Treatment Group – Treated Population

Laboratory Parameter	Time Point	Treatment Group	N	Severe/ Grade 3		Life Threatening/ Grade 4	
				n	%	n	%
Any Parameter	Baseline	Remdesivir	x	x	x	x	x
		Placebo	x	x	x	x	x
	Day 3	Remdesivir	x	x	x	x	x
		Placebo	x	x	x	x	x
	Day 5	Remdesivir	x	x	x	x	x
		Placebo	x	x	x	x	x
	Day 8	Remdesivir	x	x	x	x	x
		Placebo	x	x	x	x	x
	Day 11	Remdesivir	x	x	x	x	x
		Placebo	x	x	x	x	x
	Day 15	Remdesivir	x	x	x	x	x
		Placebo	x	x	x	x	x
	Day 29	Remdesivir	x	x	x	x	x
		Placebo	x	x	x	x	x
	Maximum Severity Post Baseline	Remdesivir	x	x	x	x	x
		Placebo	x	x	x	x	x

Each parameter will be summarized individually similar to the above...

The “Max Post Baseline” rows indicate the maximum severity experienced by each subject at any time point post baseline, including unscheduled assessments.

N = Number of subjects in the Treated Population

Table 66: Summary Statistics of Laboratory Results by Parameter, Study Visit Day, and Treatment Group – Treated Population

Laboratory Parameter	Study Visit Day	Treatment Group	Absolute					Change from Baseline				
			N	Mean	SD	Median	Min, Max	N	Mean	SD	Median	Min, Max
Parameter 1	Baseline	Remdesivir	x	xx.x	xx.x	xx.x	xx.x, xx.x	---	---	---	---	---
		Placebo	x	xx.x	xx.x	xx.x	xx.x, xx.x	---	---	---	---	---
	Day 3	Remdesivir	x	xx.x	xx.x	xx.x	xx.x, xx.x	x	xx.x	xx.x	xx.x	xx.x, xx.x
		Placebo	x	xx.x	xx.x	xx.x	xx.x, xx.x	x	xx.x	xx.x	xx.x	xx.x, xx.x
	Day 5	Remdesivir	x	xx.x	xx.x	xx.x	xx.x, xx.x	x	xx.x	xx.x	xx.x	xx.x, xx.x
		Placebo	x	xx.x	xx.x	xx.x	xx.x, xx.x	x	xx.x	xx.x	xx.x	xx.x, xx.x
	Day 8	Remdesivir	x	xx.x	xx.x	xx.x	xx.x, xx.x	x	xx.x	xx.x	xx.x	xx.x, xx.x
		Placebo	x	xx.x	xx.x	xx.x	xx.x, xx.x	x	xx.x	xx.x	xx.x	xx.x, xx.x
	Day 11	Remdesivir	x	xx.x	xx.x	xx.x	xx.x, xx.x	x	xx.x	xx.x	xx.x	xx.x, xx.x
		Placebo	x	xx.x	xx.x	xx.x	xx.x, xx.x	x	xx.x	xx.x	xx.x	xx.x, xx.x
	Day 15	Remdesivir	x	xx.x	xx.x	xx.x	xx.x, xx.x	x	xx.x	xx.x	xx.x	xx.x, xx.x
		Placebo	x	xx.x	xx.x	xx.x	xx.x, xx.x	x	xx.x	xx.x	xx.x	xx.x, xx.x
	Day 29	Remdesivir	x	xx.x	xx.x	xx.x	xx.x, xx.x	x	xx.x	xx.x	xx.x	xx.x, xx.x
		Placebo	x	xx.x	xx.x	xx.x	xx.x, xx.x	x	xx.x	xx.x	xx.x	xx.x, xx.x

Continue for all parameters...

N = Number of subjects in the Treated Population with laboratory data available for the parameter at the specified study visit.

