1.2 Schedule of Assessments

Table 1. Schedule of Assessments (SOA)

Day +/- Window	Screen	Baseline	Study Intervention Period	Follow-up Visits		
	-1 or 1	1	Daily until hospital discharge	15 ⁷ ± 2	22 ⁷ ± 3	29 ⁷ ± 3
ELIGIBILITY						
Informed consent	X					
Demographics & Medical History	X					
Targeted physical exam	X					
Review SARS-CoV-2 results	X					
STUDY INTERVENTION						
Randomization		X				
Administration of remdesivir or control		Daily until discharge or 10 days. No study product given after Day 10.				
STUDY PROCEDURES						
Vital signs including SpO ₂		X ⁴	Daily until discharge	X ⁷		X ⁷
Clinical data collection ¹		X ⁴	Daily until discharge	X ⁷	X ⁷	X ⁷
Adverse event evaluation		X ⁴	Daily until discharge	X ⁷	X ⁷	X ⁷
Concomitant medication review		X ⁴	From Day -7 to Day 11			
SAFETY LABORATORY						
Safety hematology, chemistry and liver tests	X ^{2,3}	X ^{4,5,6}	Day 3, 5, 8, 11 (all ± 1 day) if hospitalized ^{5,6}	X ⁷		X ⁷
Pregnancy test for females of childbearing potential	X ^{2,3}					
RESEARCH LABORATORY						
Blood for plasma to test for PCR SARS-CoV-2		X ⁵	Day 3, 5, 8, 11 (all ± 1 day) if hospitalized			
Oropharyngeal swab ⁸		X ⁵	Day 3, 5, 8, 11 (all ± 1 day) if hospitalized	X ⁷		X ⁷
Blood for serum (secondary research)		X ⁵	Day 3, 5, 8, 11 (all ± 1 day) if hospitalized	X ⁷		X ⁷

Notes:

¹ Refer to Section 8.1 of the protocol for details of clinical data to be collected including ordinal score, NEWS, oxygen requirement, mechanical ventilator requirement, etc.

² Screening laboratory tests include: ALT, AST, creatinine (and calculate an estimated glomerular filtration rate (eGFR) the formula used is determined by the sites, but should be consistent throughout the study), and pregnancy test.

³ Laboratory tests performed in the 48 hours prior to enrollment will be accepted for determination of eligibility.

⁴ Baseline assessments should be performed prior to first infusion. Laboratory tests performed as part of routine clinical care in the 24 hours prior to first dose will be accepted for the baseline safety laboratory tests. Baseline may be the same as the screening laboratory tests.

⁵ Safety laboratory tests include WBC with differential, hemoglobin, platelets, creatinine, glucose, total bilirubin, ALT, AST, and PT.

[figure not shown]
⁶ Any laboratory tests performed as part of routine clinical care within the specified visit window can be used for safety laboratory testing. Window during the 10 days of dosing is ±1 day.

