Subjects will be assessed daily while hospitalized. If the subjects are discharged from the hospital, they will have a study visit at Days 15, 22, and 29. For discharged subjects, it is preferred that the Day 15 and 29 visits are in person to obtain safety laboratory tests and OP swab and blood (serum only) samples for secondary research as well as clinical outcome data. However, infection control or other restrictions may limit the ability of the subject to return to the clinic. In this case, these visits may be conducted by phone, and only clinical data will be obtained. The Day 22 visit does not have laboratory tests or collection of samples and may also be conducted by phone.

The primary outcome is time to recovery by Day 29. The primary analysis will include data from both severity groups using a stratified log-rank test. A key secondary outcome evaluates treatment-related improvements in the 8-point ordinal scale at Day 15. As little is known about the clinical course of COVID-19, an evaluation of the pooled (i.e., blinded to treatment assignment) proportion recovered will be used to gauge whether the targeted total number of subjects in the recovered categories of the ordinal scale will be achieved with the planned sample size. The analysis of the pilot data will be blinded, allowing for the pilot data to be included in subsequent analyses.

The study will randomize subjects 1:1 to placebo or investigational product. In absence of an established treatment, the use of placebo is justified. If additional arms are added to or dropped from the trial, randomization will proceed with an equal probability of assignment to each of the

remaining arms. Randomization will be stratified by site and severity (severe versus mild-moderate). See Section 4.2.3 for more information on randomization and stratification.

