7. STUDY SUBJECTS

7.1. Disposition of Subjects

A summary of the reasons that subjects were screened but not enrolled will be tabulated (Table 7).

The composition of analysis populations, including reasons for subject exclusion will be summarized by treatment group and disease severity (Table 8). The summaries will be provided for both the early and full analysis sets. A subject listing of analysis population eligibilities for the early and full analysis sets will be generated (Listing 1).

The disposition of subjects will be tabulated by treatment group, disease severity and site (Table 9). Study milestones included in the table will be the total number of subjects that were screened, randomized, received a loading dose, received all expected maintenance doses, completed all expected blood draws, completed Study Day 15 visit, completed Study Day 22 visit, and completed Study Day 29 visit. In addition, the number of subjects who were unblinded to their treatment and the number of subjects with crossover remdesivir treatment will be summarized. For the calculation of percentages, subjects who die will not be included in the denominators for visits/assessments beyond their death. The number of subjects unblinded and crossover treated at each site will also be summarized (Table 10).

Treatment compliance (number of subjects who had their required infusions halted/slowed and the number of subjects with missed doses) will be summarized by treatment group (Table 11).

A flowchart showing the disposition of study subjects, adapted from the Consort Statement [4] will be generated (Figure 1). This figure will present the number of subjects screened, randomized, lost to follow-up, and analyzed, by treatment group and disease severity. This figure will be generated for both the early and full analysis sets.

A listing of subjects who discontinued dosing or terminated study follow-up and the reason will be generated (Listing 2).

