Table 7: Ineligibility Summary of Screen Failures

Inclusion/Exclusion Category	Inclusion/Exclusion Criterion	n^a	%^b
All Subjects	Total number of subjects failing any eligibility criterion or were eligible but not enrolled	x	100
Inclusion and Exclusion	Number of subjects failing any eligibility criterion	x	xx
Inclusion	Any inclusion criterion	x	xx
	[inclusion criterion 1]	x	xx
	[inclusion criterion 2]	x	xx
	[inclusion criterion 3]	x	xx
Exclusion	Any exclusion criterion	x	xx
	[exclusion criterion 1]	x	xx
	[exclusion criterion 2]	x	xx
	[exclusion criterion 3]	x	xx
Eligible but Not Enrolled		x	xx
^a More than one criterion may be marked per subject. ^b Denominator for percentages is the total number of screen failures.			

Programming Notes;

Protocol Version 3.0 included an additional inclusion criteria; footnote the addition of the inclusion/exclusion criteria based on protocol version and specify date it occurred and how many subjects were under the previous version of the criteria.

Subjects who are eligible but not enrolled will be counted in the denominator.

Table 8: Analysis Population Eligibilities by Treatment Group and Disease Severity

Analysis Population	Inclusion / Reason for Exclusion	Remdesivir (N=X)				Placebo (N=X)				All Subjects (N=X)			
		Mild-Moderate (N=X)		Severe (N=X)		Mild-Moderate (N=X)		Severe (N=X)		Mild-Moderate (N=X)		Severe (N=X)	
		n	%	n	%	%	n	n	%	n	%	n	%
Intention-to-Treat Population	Included in Population	x	xx	x	XX	x	xx	x	xx	x	xx	x	xx
Treated Population	Included for Population	x	xx	x	XX	x	xx	x	xx	x	xx	x	xx
	Excluded from Population	x	xx	x	XX	x	xx	x	xx	x	xx	x	xx
	Did Not Receive at least one Infusion	x	xx	x	XX	x	xx	x	xx	x	xx	x	xx

N = Number of subjects randomized to the specified arm/disease severity stratum

Table 9: Subject Disposition by Treatment Group and Disease Severity

Subject Disposition	Remdesivir (N=X)				Placebo (N=X)				All Subjects (N=X)			
	Mild-Moderate (N=X)		Severe (N=X)		Mild-Moderate (N=X)		Severe (N=X)		Mild-Moderate (N=X)		Severe (N=X)	
	n	%	n	%	n	%	n	%	n	%	n	%
Randomized	x	100	x	100	x	100	x	100	x	100	x	100
Received Loading Dose	x	xx	x	xx	x	xx	x	xx	x	xx	x	xx
Completed All Blood Draws	x	xx	x	xx	x	xx	x	xx	x	xx	x	xx
Completed All OP swab collections	x	xx	x	xx	x	xx	x	xx	x	xx	x	xx
Completed Follow-up (Study Day 8)	x	xx	x	xx	x	xx	x	xx	x	xx	x	xx
Completed Follow-up (Study Day 11)	x	xx	x	xx	x	xx	x	xx	x	xx	x	xx
Completed Follow-up (Study Day 15)	x	xx	x	xx	x	xx	x	xx	x	xx	x	xx

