Completed Follow-up (Study Day 22)	x	xx	x	xx	x	xx	x	xx	x	xx	x	xx
Completed Follow-up (Study Day 29)	x	xx	x	xx	x	xx	x	xx	x	xx	x	xx
Unblinded during follow-up	x	xx	x	xx	x	xx	x	xx	x	xx	x	xx
Retreated with Remdesivir during follow-up	-	-	-	-	x	xx	x	xx	x	xx	x	xx

N= Number of subjects enrolled

Programming Notes:

To count a subject as completing all blood draws, a subject had to have the following questions from the visit CRFs answered as a Yes or NA (not required) up through their discharge/death:

- Was blood collected for hematology, chemistry, and/or liver tests?
- Was blood drawn for PCR assays?

Note: in LB – there should be a result in LBSTRESN for each visit or LBSTAT=NOT DONE and LBREASND = Not required.

To count a subject as completing all OP swab collections, a subject had to have the following question from the visit CRFs answered as a Yes or N/A (not required) up through their discharge/death.

- Was oropharyngeal swab collected?
- Was a swab collected for viral load and/or shedding

To count a subject for each Study Day, the subject had to complete the visit for that day. Study Day 8 = VISITNUM=108, Study Day 11 = VISITNUM=111, Study Day 15 = VISITNUM=115, Study Day 22 = VISITNUM=122, Study Day 29 = VISITNUM=129

Table 10: Subject Unblinding and Crossover Treatment by Site

Site	Number of Subjects Unblinded	Number of Subjects Crossover Treated
Site 1	x	x
Site 2	x	x
Site 3	x	x
Site 4	x	x
Site 5	x	x
...

Programming Notes: Only sites with at least one unblinded subject will be included in the table.

Table 11: Treatment Compliance by Treatment Group

Disposition	Remdesivir (N=X)			Placebo (N=X)			All Subjects (N=X)			Proportion Difference	
	n	%	95%CI ^a	n	%	95%CI	n	%	95%CI	%	95%CI
Received Loading Dose	x	x	x.x, x.x	x	x	x.x, x.x	x	x	x.x, x.x	x	x.x, x.x
Completed all 10 Infusions	x	x	x.x, x.x	x	x	x.x, x.x	x	x	x.x, x.x	x	x.x, x.x
Completed less than 10 Infusions due to Discharge	x	x	x.x, x.x	x	x	x.x, x.x	x	x	x.x, x.x	x	x.x, x.x
Completed less than 10 Infusions due to Death	x	x	x.x, x.x	x	x	x.x, x.x	x	x	x.x, x.x	x	x.x, x.x
Had Any Infusions Halted or Slowed	x	x	x.x, x.x	x	x	x.x, x.x	x	x	x.x, x.x	x	x.x, x.x
Missed Any Maintenance Dose	x	x	x.x, x.x	x	x	x.x, x.x	x	x	x.x, x.x	x	x.x, x.x

N = Number of subject enrolled
A required infusion is counted as complete even if it was halted or slowed. A required full infusion is counted as completed as long as it was not halted nor slowed.
95% CI for proportions obtained by Clopper-Pearson

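### SAP Table 9 counts subjects discharged before Day 8 or Day 11 as not completing follow-up at those days, although no visit was due

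*SAP*

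**What the plan says.** **Numerator.** The Table 9 shell in SAP Appendix 1 has the rows "Completed Follow-up (Study Day 8)" and "Completed Follow-up (Study Day 11)". The programming note below it states: "To count a subject for each Study Day, the subject had to complete the visit for that day". It ties Day 8 to visit number 108 and Day 11 to visit number 111.

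**Denominator.** The shell footnote reads "N= Number of subjects enrolled". SAP 7.1 makes one adjustment for percentages: "subjects who die will not be included in the denominators for visits/assessments beyond their death". It does not mention discharge.

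**Schedule.** SAP 4.1 says "Subjects will be assessed daily while hospitalized", and then: "If the subjects are discharged from the hospital, they will have a study visit at Days 15, 22, and 29". The schedule in Protocol 1.2 heads the in-hospital column "Daily until hospital discharge", and the Day 8 and Day 11 laboratory tests and swabs are due only in subjects still in hospital. Protocol 8.1.2.2 likewise ends the daily ordinal score at discharge if that comes before Day 11.

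**Neighbouring rows.** The same programming note treats a blood draw or swab as complete if it was done or was not required, up to discharge or death. The visit rows have no such allowance. The milestones listed in the text of SAP 7.1 include the Day 15, 22 and 29 visits but not Day 8 or Day 11.

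**The concern.** Read together, these rules put a subject who went home on Day 6 into the Day 8 and Day 11 denominators with no possibility of entering the numerators. The row is labelled as completed follow-up, but its value falls with every discharge as well as with every missed visit.

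The trial is designed to detect faster recovery on remdesivir, and recovery includes discharge. If the drug works as the design assumes, these two rows will show a lower completion percentage on remdesivir even if no subject is lost. What is at stake is a correct reading of two rows in a descriptive disposition table.

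**Working it through.** The documents state no figure for these rows, so there is none to reproduce. The check has two parts: the effect of the rule itself, then an illustration of its size.

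**1. The rule, in a simple example.** Take 100 subjects in one arm (invented numbers). By Day 8, 5 have died, 20 have been discharged, and the remaining 75 all attend.

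- As written, removing deaths only: 75 / (100 − 5) = 78.9%.
- Removing deaths and discharges: 75 / (100 − 5 − 20) = 100%.

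Nobody was lost; the whole shortfall is discharge.

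**2. Inputs for the size.**

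- Recovery rate ratio 1.35, needing 400 recoveries for 85% power (SAP 5, Protocol 9.2). The documents' event formula gives 399, which agrees.
- Pooled recovery by Day 29 of 70%, giving 572 subjects (Protocol 9). 400 / 0.70 = 571.4, which agrees.
- Assumptions that are not in the documents: exponential times from Day 1, discharge at recovery, no deaths, no missed visits, and no visit record created after discharge.

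**3. Formulas.** Day 29 is 28 days after Day 1, Day 8 is 7 days and Day 11 is 10 days. With control hazard λ, the share still in hospital after t days is exp(−λt) on placebo and exp(−1.35λt) on remdesivir. Under the assumptions this share is what the row would report as completed. The hazard solves

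1 − [exp(−28λ) + exp(−1.35 × 28λ)] / 2 = 0.70, so λ = 0.0371 per day.

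**4. Main illustration.**

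| Row | Placebo | Remdesivir | False gap |
|---|---|---|---|
| Day 8 (t = 7) | 77.1% | 70.4% | 6.7 points |
| Day 11 (t = 10) | 69.0% | 60.6% | 8.4 points |

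**5. Sensitivity to early discharge.** Exclusion criterion 4 bars patients expected to leave within 72 hours, which argues against a constant hazard from Day 1. With no discharge in the first 3 days, the same 70% is reached over 25 days, so λ = 0.0415. The exposure times become 4 and 7 days.

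| Row | Placebo | Remdesivir | False gap |
|---|---|---|---|
| Day 8 | 84.7% | 79.9% | 4.8 points |
| Day 11 | 74.8% | 67.5% | 7.2 points |

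**6. Sensitivity to recovery and discharge rates.** Some subjects recover while still in hospital (category 3), so discharge may lag recovery. Returning to a constant hazard from Day 1, with pooled recovery of 60–80% and a discharge hazard of 75–100% of the recovery hazard, the false gap is 4.3 to 8.1 points at Day 8 and 5.8 to 9.7 points at Day 11.

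**7. After the fix.** With subjects alive and still in hospital as the denominator, or with discharged subjects counted as not requiring the visit, every case in steps 4 to 6 gives 100% in both arms and a gap of 0.

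**The case against.** The strongest reply is that the consequences are small. Most of it stands.

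- **The table partly corrects itself.** Discharged subjects do have Day 15, 22 and 29 visits, and those rows come next. With perfect follow-up they would return to about 100%, and true attrition does not reverse.
- **Real losses are shown elsewhere.** The CONSORT figure gives loss to follow-up by arm and severity, and Listing 2 gives early terminations with reasons. Table 34 has a separate line for discharged subjects without a score at each visit, including Days 8 and 11.
- **The rows have little standing.** SAP 7.1 does not list them as milestones, and SAP 17 allows the final presentation to differ from the shells.
- **A database rule could reduce the effect.** The documents do not say whether a visit 108 or 111 record exists for a discharged subject. If it does, the effect shrinks.

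These points limit the harm. They do not make the stated rule correct, since the blood-draw and swab rows of the same table already make the needed allowance.

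Two stronger readings are tempting and are not supported. A reader might infer differential loss to follow-up that threatens the primary endpoint. But SAP 3.3.2 counts a subject discharged without a recovery score as recovered at discharge, so for that endpoint these subjects have already had their event. A reader might also take the mild-disease Scenario 2 in Protocol Table 5 and project a Day 11 row near 30%. That scenario has 9 + 36 + 45 = 90% in the recovered categories by Day 15, which does not fit the plan's 70% by Day 29.

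**Conclusion.** The point holds as a minor fault in a table shell. As written, the Day 8 and Day 11 rows mix discharge with missed visits and would show lower completion in the arm that goes home sooner. Under the plan's own rate ratio and recovery proportion, the false gap is about 7 points at Day 8 and 8 at Day 11, or about 5 and 7 if discharge starts only after three days. Those figures rest on the assumptions listed above, the main ones being discharge at recovery and no visit record after discharge; they are not predictions.

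The effect stops at these two rows. The Day 15, 22 and 29 rows, the CONSORT figure, Listing 2 and all efficacy and safety analyses are unaffected.

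**What to change.** Change the Table 9 programming note in one of three ways:

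- use as the denominator for the Day 8 and Day 11 rows the subjects alive and still in hospital on that day, and label the rows accordingly;
- count discharged subjects as not requiring the visit, as the note already does for blood draws and swabs; or
- drop the two rows, so that the shell matches the milestones in SAP 7.1.

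The first is the most informative, because it shows actual missed in-hospital visits. The cost is one line of programming specification, with no new data collection and no change to any inferential analysis.

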7. STUDY INTERVENTION DISCONTINUATION AND SUBJECT DISCONTINUATION/WITHDRAWAL

7.1 Halting Criteria and Discontinuation of Study Intervention

7.1.1 Individual Infusion Halting

See Section 6.1.4. for information about dosing modifications due to laboratory abnormalities.

For an individual subject, an individual infusion must be stopped if they have a suspected drug-related event of hypersensitivity (Grade 2 or higher) during the infusion. While there are no criteria

for grading “hypersensitivity” in the Division of AIDS (DAIDS) Table for Grading the Severity of Adverse Events, sites should use acute allergic reaction from that toxicity table. Subjects who have an IV infusion stopped for a safety related issues will not continue with dosing.

The treatment of any given subject may be stopped for SAEs, clinically significant adverse events, severe laboratory abnormalities, or any other medical conditions that indicate to the Investigator that continued dosing is not in the best interest of the patient.

In addition, a subject in this clinical study may discontinue study drug at their request for any reason. Every effort should be made to encourage subjects to remain in the study for the duration of their planned outcome assessments. Subjects should be educated on the continued scientific importance of their data, even if they discontinue study drug.

Unless the subject withdraws consent, those who discontinue study drug early will remain in the study. The reason for subject discontinuation of study drug should be documented in the case report form.

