6.3.1. Intention-to-Treat (ITT) and Treated Populations

The intent-to-treat (ITT) population includes all subjects who were randomized.

The treated population includes all randomized subjects who received any study drug infusion, even if the infusion was halted or slowed.

For the main analyses of the primary and secondary efficacy outcomes, subjects in both populations will be classified by the treatment arm and disease severity stratum to which they were randomized. For safety, subgroup, and sensitivity analyses, subjects may be classified by their randomized or actual disease severity and placebo subjects who cross over and are treated with remdesivir will be censored/excluded as described in Section 3 and Section 8.

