95% CI for difference in proportions obtained by the exact method

Programming Notes:

Received Loading Dose: Subjects received the first treatment: EC.ECTPT = DOSE 1, EC.ECPSTRG=200, ECADJ is missing.

Had any infusions halted or slowed: EC.ECADJ is not missing through day 10 or through discharge from hospital or death.

Missed any maintenance dose: EC.ECOCCUR=N through day 10 or through discharge from hospital or death.

95% CI for proportions obtained by Clopper-Pearson:

```
proc freq;
    Table treatment*analysisvariable / binomial;
    ods output binomialcls=outputdsn;
run;
```

95% CI for difference in proportions obtained by the exact method:

```
proc freq;
    Table treatment*analysisvariable / riskdiff (cl=exact);
run;
```

Table 12: Distribution of Protocol Deviations by Category, Type, Treatment Group, and Disease Severity

Category	Deviation Type	Remdesivir (N=X)				Placebo (N=X)				All Subjects (N=X)			
		Mild-Moderate (N=X)		Severe (N=X)		Mild-Moderate (N=X)		Severe (N=X)		Mild-Moderate (N=X)		Severe (N=X)	
		# of Subj.	# of Dev.	# of Subj.	# of Dev.	# of Subj.	# of Dev.	# of Subj.	# of Dev.	# of Subj.	# of Dev.	# of Subj.	# of Dev.
Eligibility/enrollment	Any type	x	x	x	x	x	x	x	x	x	x	x	x
	Did not meet inclusion criterion	x	x	x	x	x	x	x	x	x	x	x	x
	Met exclusion criterion	x	x	x	x	x	x	x	x	x	x	x	x
	ICF not signed prior to study procedures	x	x	x	x	x	x	x	x	x	x	x	x
	Other	x	x	x	x	x	x	x	x	x	x	x	x
Treatment administration schedule	Any type	x	x	x	x	x	x	x	x	x	x	x	x
	Out of window visit	x	x	x	x	x	x	x	x	x	x	x	x
	Missed visit/visit not conducted	x	x	x	x	x	x	x	x	x	x	x	x
	Missed treatment administration	x	x	x	x	x	x	x	x	x	x	x	x
	Delayed treatment administration	x	x	x	x	x	x	x	x	x	x	x	x
Other	x	x	x	x	x	x	x	x	x	x	x	x	
Follow-up visit schedule	Any type	x	x	x	x	x	x	x	x	x	x	x	x
	Out of window visit	x	x	x	x	x	x	x	x	x	x	x	x
	Missed visit/visit not conducted	x	x	x	x	x	x	x	x	x	x	x	x
	Other	x	x	x	x	x	x	x	x	x	x	x	x
Protocol procedure/assessment	Any type	x	x	x	x	x	x	x	x	x	x	x	x
	Incorrect version of ICF signed	x	x	x	x	x	x	x	x	x	x	x	x
	Blood not collected	x	x	x	x	x	x	x	x	x	x	x	x
	Oropharyngeal swab not collected	x	x	x	x	x	x	x	x	x	x	x	x
	Other specimen not collected	x	x	x	x	x	x	x	x	x	x	x	x
	Specimen result not obtained	x	x	x	x	x	x	x	x	x	x	x	x
Required procedure not conducted	x	x	x	x	x	x	x	x	x	x	x	x	

Category	Deviation Type	Remdesivir (N=X)				Placebo (N=X)				All Subjects (N=X)			

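### SAP Table 11 would record a first infusion that was started but halted or slowed as a loading dose not received; separately, no table gives stopped or suspended dosing by arm

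*SAP*

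**What the plan says.** SAP Appendix 1, Table 11 summarises treatment compliance by arm, with a Clopper-Pearson interval for each percentage and an exact interval for each arm difference. Its programming notes define the first row: "Received Loading Dose: Subjects received the first treatment: EC.ECTPT = DOSE 1, EC.ECPSTRG=200, ECADJ is missing". The following note defines the adjustment row: "Had any infusions halted or slowed: EC.ECADJ is not missing through day 10 or through discharge from hospital or death".

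The table's footnote has two sentences on counting. The first is "A required infusion is counted as complete even if it was halted or slowed". The second is "A required full infusion is counted as completed as long as it was not halted nor slowed".

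SAP 6.3.1 defines who counts as treated: "The treated population includes all randomized subjects who received any study drug infusion, even if the infusion was halted or slowed".

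On reasons for a short course, Table 11 has two rows: "Completed less than 10 Infusions due to Discharge" and "Completed less than 10 Infusions due to Death". Its other rows cover completing all ten infusions, any halted or slowed infusion, and any missed maintenance dose. SAP 3.1 and 4.3, like Protocol Section 3, name the stopping or temporary suspension of infusions, whatever the reason, as a safety measure. SAP 3.1 and Protocol Section 3 frame it as a comparison with the control arm.

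**The concern.** A reader takes *Received Loading Dose* to mean that the first infusion was given. Under the written rule, a subject whose first infusion was started and then slowed fails the ECADJ condition and drops out of the row. The same subject is treated under SAP 6.3.1 and has a complete infusion under the footnote's first sentence.

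Two things are at stake. First, the row prints an arm difference with an interval. If first infusions were adjusted more often in one arm, the table would show that arm as having received less treatment when every subject was started. Second, a stated safety measure has no by-arm count. Table 11 pools halted with slowed, gives only discharge and death as reasons for a short course, and counts missed doses without a reason.

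**Working it through.** **Reading the rule.** This is a derivation rule, so the plan has no figure of its own to reproduce. Take one subject in whom dose 1 was started and slowed and nine further infusions were given:

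| Place in the SAP | How the subject is counted |
|---|---|
| Table 11 note, *Received Loading Dose* (ECADJ must be missing) | Not received |
| Table 11 note, halted-or-slowed row (ECADJ not missing) | Counted |
| Table 11 footnote, first sentence | Infusion complete, so the subject has ten completed infusions |
| SAP 6.3.1 and Table 8 | In the Treated population |

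Table 11 would therefore show this subject as having completed all ten infusions without receiving the first. The footnote's second sentence sets a stricter full-infusion count that matches the ECADJ condition, but no row of Table 11 carries the label *full*. Table 9 has a row with the same name, and its programming notes give no rule for it, so Tables 9 and 11 could also differ.

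**Size of the error.** Inputs:
- n = 286 per arm, half of the 572 subjects projected in Protocol Section 9 (400 / 0.70 = 571.4, rounded up to 572; 572 / 2 = 286).
- All n subjects in each arm start dose 1 (assumption).
- The shares of first infusions halted or slowed, r on remdesivir and p on placebo. The documents give neither, so a range is shown.

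Printed count = n − A, where A is the number of adjusted first infusions, rounded to a whole subject. Printed difference = (A on placebo − A on remdesivir) / n. The true difference is 0.

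| r vs p (assumed) | A, remdesivir vs placebo | Printed, remdesivir | Printed, placebo | Printed difference |
|---|---|---|---|---|
| 0% vs 0% | 0 vs 0 | 286/286 = 100% | 286/286 = 100% | 0 |
| 1% vs 1% | 3 vs 3 | 283/286 = 99.0% | 283/286 = 99.0% | 0 |
| 2% vs 1% | 6 vs 3 | 280/286 = 97.9% | 283/286 = 99.0% | -3/286 = -1.0 points |
| 5% vs 1% | 14 vs 3 | 272/286 = 95.1% | 283/286 = 99.0% | -11/286 = -3.8 points |
| 5% vs 5% | 14 vs 14 | 272/286 = 95.1% | 272/286 = 95.1% | 0 |
| 10% vs 2% | 29 vs 6 | 257/286 = 89.9% | 280/286 = 97.9% | -23/286 = -8.0 points |

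For 5% against 1%, the Clopper-Pearson 95% intervals are 91.9 to 97.3 and 97.0 to 99.8. With the ECADJ condition removed, every line reads 286/286 = 100% (98.7 to 100) in each arm. Exact intervals for the differences were not computed.

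**Is stopped or suspended dosing counted by arm elsewhere?**
- Table 57 counts adverse events leading to early termination. Listing 2 keeps early termination and treatment discontinuation as separate categories, and Protocol 7.1.1 keeps subjects who stop the drug in the study.
- The safety composite names discontinuation of infusions in the heading of SAP 3.3.11 and in the Table 64 footnote, but the components listed in 3.3.11 omit it. A composite would not isolate it in any case.
- Listings 2 and 10 give reasons, and Listings 11 to 13 give the action taken with study treatment. All of these are subject by subject.

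No table gives the count by arm.

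**The case against.** The strongest reply has four parts.

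*The row may be meant as a full loading dose.* The footnote's second sentence supports a stricter category, and its first sentence speaks of infusions being complete rather than received. This stands as a possible account of how the rule arose. It does not rescue the row, whose label says only that the dose was received. Relabelling would be a legitimate cure, but Table 11 would then have no count of loading doses started.

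*The damage is confined.* This stands. A reader might infer that dose exposure and tolerability by arm are misreported in general. The documents do not support that: the adjusted subjects still appear by arm in the halted-or-slowed row, and neither the Treated population nor the adverse event denominators use the rule. That these subjects appear in the other row is not double counting, because the rows are not mutually exclusive.

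*Listings are allowed.* Protocol 9.4.4 permits either a table or a listing for adverse events that lead to stopping the intervention, and SAP Section 17 allows extra summaries. So the missing by-arm rows are not an error. But 9.4.4 does not address suspensions or stops for other reasons, and a listing is not the comparison with control that SAP 3.1 describes.

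*The clinical reading goes too far.* A reader might infer that the subjects dropped from the row are those who reacted to the infusion. Nothing ties every ECADJ entry to a reaction, and Listing 10 exists to record the reason. Nor does Protocol 7.1.1 contrast halting with slowing. It says "Subjects who have an IV infusion stopped for a safety related issues will not continue with dosing" and does not mention slowing. Finally, the SAP does not say whether missed-dose records are created after permanent discontinuation, so it cannot be said that every such subject would fall into the missed-dose row.

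**Conclusion.** The concern holds for one descriptive row. As written, *Received Loading Dose* in Table 11 is understated by the number of first infusions that were started and then halted or slowed. This contradicts the row's label, the footnote's first sentence and SAP 6.3.1. The conclusion rests on the SAP's own notes and on the assumption that ECADJ has the same meaning in both.

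The size is unknown. It is zero if no first infusion was adjusted, and a false arm difference needs unequal rates; the -3.8 points at 5% against 1% is an illustration, not an estimate. No efficacy result changes.

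The lack of a by-arm count of discontinued or suspended dosing is a separate and weaker point. The information is planned in listings, so this is a gap in summary and not a misreport.

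**What to change.** 1. In the Table 11 notes, define *Received Loading Dose* as dose 1 started, regardless of ECADJ. Apply the same rule to the row of that name in Table 9.
2. If a count of unadjusted first infusions is wanted, add a separately labelled row, *Full loading dose*, that requires ECADJ to be missing. This also gives the footnote's second sentence a row to refer to.
3. As an addition, report halted and slowed infusions in separate rows. Add by-arm rows for dosing discontinued early (adverse event or laboratory abnormality; other reason) and for infusions withheld and later resumed, with differences and intervals as for the other rows.

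The cost is an edit to the Table 11 shell and notes and one line in the Table 9 notes. The reasons are already called for in Listings 2 and 10, so no new data are needed. The only downside is a slightly longer table.
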